**[contact]**

**[[contact]](mailto:[contact])**

## **1.0 Objectives**

The goal of this prospective observational pilot study is to evaluate the tolerability and safety of RESTASIS (cyclosporine ophthalmic solution 0.05%) when added to the PROSE (Prosthetic Replacement of the Ocular Surface Ecosystem) lens reservoir in patients with ocular surface disease (OSD). Secondary endpoints include early (1-month) efficacy data for ocular signs and symptoms.

## **2.0 Background**

PROSE treatment is for individuals with irregular ocular surfaces that require a rigid lens to mask irregularities on the front refracting surface of their eye, the cornea. As well, and more relevant to this study, PROSE treatment is used for cases of ocular surface disease to protect and support the ocular surface to reduce dryness and prevent ocular surface breakdown, which can lead to ulceration and perforation. The PROSE device is like a scleral lens in theory though it allows for unique customizations of the fit that are unavailable in currently marketed scleral lens designs. Traditional commercial scleral lenses as well as PROSE serve a therapeutic purpose by bathing the ocular surface with normal saline, also known as 0.9% sodium chloride solution, which provides constant lubrication and protection. Because this liquid is maintaining contact with the cornea and ocular surface for long periods of time as the lens is on the eye, the concept of using the device for drug delivery via addition of a preservative-free topical medication to the scleral lens bowl along with saline has been explored in various publications.

Per the TFOS DEWS II published in 2017, dry eye syndrome (also known as ocular surface disease) is defined as a “multifactorial disease of the ocular surface characterized by a loss of homeostasis of the tear film, and accompanied by ocular symptoms, in which tear film instability and hyperosmolarity, ocular inflammation and damage, and neurosensory abnormalities play etiological roles.” Dry eye is often categorized as aqueous deficient (stemming from issues with the lacrimal gland itself, usually categorized as Sjogren’s and Non-Sjogren’s) or evaporative (stemming from issues with the meibomian glands that produce the lipid layer of the tear film) or mixed mechanism involving both aqueous and evaporative components.

Outcomes will include subjective responses regarding the subject’s symptoms and visual function in addition to the objective assessments of the health of the ocular surface seen on clinical examination. Results will be measured at baseline, after 1 week, and after 1 month of the study.

### **3.0 Inclusion and Exclusion Criteria**

The participant will be eligible to participate if the following criteria apply:

1. Written Informed Consent has been obtained prior to any study-related procedures taking place
2. Subject is Male or Female, 18 years of age or older prior to the initial visit
3. Is an established wearer of PROSE devices for > 6 months in both eyes

4. Has a finalized PROSE lens design in both eyes, in the opinion of the clinician
5. The PROSE design does NOT include fenestrations
6. Subject requires PROSE devices to treat symptoms and/or signs from underlying dry eye disease, GVHD, Sjogren's syndrome, limbal stem cell deficiency, keratoconjunctivitis sicca, or ocular surface disease
7. Baseline Corneal staining grade of 2 or higher in total, both eyes combined (NEI Grading System)
8. Baseline Ocular Surface Disease Index 13 or greater
9. In the opinion of the investigator, the subject can follow study instructions
10. In the opinion of the investigator, the subject can complete all study procedures and visits
11. Able to wear PROSE device continuously for at least 6 hours at a time without removal, in each eye
12. Able to wear PROSE device for at least 10 total hours a day, in each eye
13. Able to wear PROSE device in subsequent continuous sessions of 6 hours, followed by a break to re-instill Restasis in device bowl, followed by another period of continuous wear of at least 4 hours
14. Currently using buffered preservative free normal saline (Purilens) in the device bowl or willing to transition to buffered preservative free normal saline (Purilens) use in the device bowl during the study

The participant would NOT be eligible to participate if at least one of the following criteria is met:

1. Is currently participating in any other type of eye-related clinical or research study
2. Is pregnant or nursing as reported by the subject.
3. Has a condition or is in a situation which, in the investigator's opinion, may put the subject at significant risk, may confound study outcomes, or may significantly interfere with the subject's participation in the study.
4. Has had previous ocular surgery within the past 12 weeks.
5. Currently uses or has a prior history of using Restasis in the last 3 months
6. Currently uses or has a prior history of using Cequa in the last 3 months
7. Is currently using Xiidra and has been using Xiidra for less than 3 months
8. Has a history of an allergic reaction or hypersensitivity to any active or inactive ingredient found in Restasis or Cequa or Purilens.
9. Is wearing a PROSE device with Tangible HydraPEG coating
10. The subject is not wearing their PROSE devices daily
11. The subject is only wearing a device for one eye.
12. The participant is monocular
13. The subject wears a PROSE lens with fenestrations
14. The participant carries a diagnosis of glaucoma or ocular hypertension or glaucoma suspect AND is currently using glaucoma medications

15. The participant is NOT able to wear PROSE devices for 6 hours continuously, followed by a break to re-instill Restasis, followed by an additional period of at least 4 hours of continuous wear
16. Allergy to sodium fluorescein
17. Allergy to lissamine green
18. Allergy or intolerance to Purilens solution.

#### **4.0 Vulnerable Populations**

The following special populations will be excluded from this study:

- Adults unable to consent (including adults unable to read and understand English)
- Individuals who are not yet adults (infants, children, teenagers)
- Pregnant women
- Prisoners
- Employees of BostonSight

#### **5.0 Number of Subjects**

This study will enroll a minimum of 10 subjects. We expect an approximate 10% drop-out rate, so we will expect to recruit approximately 12 subjects; and the first 10 to be eligible and complete the study will be used for data analysis. All subjects will receive the study drug, Restasis (cyclosporine ophthalmic solution 0.05%).

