#### **7.0 Multi-Site Research Communication – N/A**

#### **8.0 Study Timelines**

The total duration of the subjects' participation in the study will be between 4-6 weeks. It is anticipated that to enroll all study subjects, it will take approximately 8 months. The estimated date for completion of this study is 12 months after the start of recruitment.

The study will enroll 2 groups of subjects:

- Group A: Those subjects already using preservative free buffered normal saline (Purilens) at the time of enrollment to the study

- Group B: Those subjects NOT currently using preservative free buffered normal saline (Purilens) at the time of enrollment but who are willing to be switched to preservative free buffered normal saline (Purilens) as part of the study protocol

Visit 1A:

- a. Completion of informed consent
- b. Collect past medical history, past ocular history, allergies, medications as well as habitual contact lens information, including lens design, power, and diameter.
- c. Subject's evaluation of symptoms via a baseline tolerability questionnaire and baseline Ocular Surface Disease Index (OSDI)
- d. Visual acuity assessments of both eyes (logMAR)
- e. Baseline assessment of PROSE device:
  - a. Confirm acceptable fit
- f. Baseline Oculus Keratograph 5M R-Scan with lens (automatic classification of redness)
- g. Remove lens
- h. Baseline Oculus Keratograph 5M R-Scan without lens (automatic classification of redness)
- i. Baseline slit lamp examination (without lens) including:
  - a. anterior segment and ocular surface
  - b. conjunctival redness (Efron Grading Scale, Modified Efron Grading Scale)
  - c. corneal staining with sodium fluorescein (NEI Grading System)
  - d. conjunctival staining with lissamine green (NEI Grading System)
- j. Initiation of study, with either:
  - a. Group A (subjects currently using Purilens): Dispense Restasis for initiation of usage in device bowl
    - i. Instructions for use: 1 drop of RESTASIS in the lens bowl followed by filling the remainder of the lens bowl with Purilens qAM. After 6 consecutive hours of wear, remove and reapply lens with 1 drop of RESTASIS in the lens bowl followed by filling the remainder of the lens bowl with Purilens. Wear lens without removal for at least 4 more consecutive hours.
  - b. Group B (subjects NOT currently using Purilens): the subject will be provided Purilens for use over the next two weeks and return for Visit 1B
- k. Reapply lens and wait 15 minutes

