### **RESTASIS (cyclosporine ophthalmic solution 0.05%) (AbbVie Inc.)**

RESTASIS (cyclosporine ophthalmic solution 0.05%) is a topical immunomodulator indicated to increase tear production in patients with ocular surface inflammation associated with keratoconjunctivitis sicca. RESTASIS appears as a translucent homogenous emulsion. The osmolarity is 230 to 320 mOsmol/kg and the pH of the solution is 6.5-8.0. RESTASIS is a FDA approved drug for the increase of tear production in patients with keratoconjunctivitis sicca (dry eye syndrome). FDA approval initially occurred in 1983 and was most recently approved as of October 2003.

The ingredients for RESTASIS are listed below:

- Active Ingredients: Cyclosporine 0.05%
- Inactive Ingredients: Glycerin, castor oil, polysorbate 80, carbomer copolymer type A, purified water, and sodium hydroxide to adjust pH.

"In clinical trials the most common adverse reaction following the use of RESTASIS® was ocular burning (17%). Other reactions reported in 1% to 5% of patients included conjunctival hyperemia, discharge, epiphora, eye pain, foreign body sensation, pruritus, stinging, and visual disturbance (most often blurring)".

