### **Adverse event reporting guidelines:**

All adverse events must be reported in the subject's source documents, and recorded on an Adverse Event Case Report Form regardless of whether or not they are considered to be related to the test article. The recording should be within 24 hours of the time that the AE came to the attention of the Investigator. For non-serious AE it is sufficient to enter the AE information into the CRF. The Clinical Research Coordinator will review the database on a regular basis.

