#### **15.0 Withdrawal of Subjects**

Subjects will be withdrawn from the study if they are unable to complete the tasks in the study protocol. In addition, if they experience an adverse event in which the investigator does not feel that the subjects should continue, they will be withdrawn.

The data from a subject that withdraws or is terminated from the study will not be included in the analysis.

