**Novel Use of Cyclosporine Ophthalmic Emulsion 0.05% in a PROSE Device**

**NCT#: NCT04918823**

**Version: 8/27/2024**

## Statistical Analysis

Statistical analysis was performed using Visual Studio Code (Microsoft Corp., Redmond WA) with python version 3.9.12. Subject data post-treatment was compared to their baseline data, collected prior to initiating use of the study drug. For Group A, the data collected at Visit 1A was considered to be their baseline data pre-intervention. For Group B, the data collected at Visit 1B was considered to be their baseline data (post-initiation of Purilens and pre-initiation of cyclosporine). The core algorithm used was based on statistical functions module `scipy.stats`. For univariate data analysis (before/after visits), paired t-test was performed since every patient received treatment. Paired t-test was conducted by `scipy.stats.ttest_rel` and <https://www.statskingdom.com/paired-t-test-calculator.html>. For bi-variate data, two-way ANOVA (Analysis of variance) was performed. Two-way ANOVA was conducted by `sm.stats.anova_lm(model)` function. The significance level was set to a P-value of  $\leq 0.05$  in all instances of analysis.

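### Protocol section 5.0 recruits about 12 subjects but analyses only the first 10 completers, so a treated subject with complete data can be left out for no stated reason

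*Protocol*

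**What the plan says.** Protocol section 5.0 opens with a floor: "This study will enroll a minimum of 10 subjects". It expects about 10% drop-out, plans to recruit approximately 12, and gives the study drug to every subject. The same section then turns the floor into a ceiling for the analysis: "the first 10 to be eligible and complete the study will be used for data analysis".

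Section 15.0 has a separate exclusion: "The data from a subject that withdraws or is terminated from the study will not be included in the analysis". It covers people who leave early, not a subject who finishes after the tenth completer.

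The SAP describes the comparison as follows: "Subject data post-treatment was compared to their baseline data, collected prior to initiating use of the study drug". It defines no analysis set and mentions neither the first-10 rule nor any departure from it. Neither document explains the cap, stops enrolment once 10 have completed, or says what happens to an 11th completer's data.

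**The concern.** The stated goal is to "evaluate the tolerability and safety of RESTASIS" when it is placed in the lens reservoir. For that question, every treated subject with baseline, 1-week and 1-month data counts. Under the rule as written, a subject can take the drug for four weeks, attend every visit, and contribute nothing to the analysed questionnaire, OSDI, acuity, staining or redness results. In a set of 10, one or two such subjects would add 10% to 20% to the sample, from data already collected.

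The rule is also not fully specified. The word first could refer to order of enrolment or order of completion, and these can select different people, because Group B spends two weeks on Purilens before starting Restasis. If completion order is meant, Group A is slightly favoured.

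**Working it through.** **Inputs from the documents.** Target of 10, drop-out of about 10%, about 12 recruits, all receiving Restasis (Protocol 5.0); enrolment over about 8 months and a two-week run-in for Group B (8.0).

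**Assumptions.** Drop-outs are independent. Drop-out rates other than 10%, and all screen-failure rates, are assumed for sensitivity.

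**The plan's own figure.** 10 / (1 − 0.10) = 11.1, rounded up to 12. The recruitment number reproduces; the problem is the cap on completers.

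**Chance of a surplus completer.** With 12 treated recruits and completion probability 0.9, the number completing is Binomial(12, 0.9):

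- P(11 complete) = 12 × 0.9^11 × 0.1 = 0.377
- P(12 complete) = 0.9^12 = 0.282
- P(at least one left out) = 0.377 + 0.282 = 0.659
- Mean number left out = 0.377 + 2 × 0.282 = 0.94

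| Drop-out (12 treated) | P(at least one completer left out) | Mean number left out |
|---|---|---|
| 5% | 0.88 | 1.42 |
| 10% | 0.66 | 0.94 |
| 15% | 0.44 | 0.59 |
| 20% | 0.27 | 0.34 |

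**If fewer or more are treated, at 10% drop-out.** With 11 treated (one screen failure among 12), the probability and the mean are both 0.9^11 = 0.31. With 10 treated, both are zero. If approximately 12 turned out to be 13, the probability would be 0.87.

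**What the surplus is worth.** The half-width of a 95% confidence interval for a mean paired change, in units of the SD of the change, is t(0.975, n−1)/√n. With no events observed, the one-sided 95% upper bound on an event rate is 1 − 0.05^(1/n).

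| n analysed | Half-width (SD) | Change from n = 10 | Zero-event upper bound |
|---|---|---|---|
| 10 | 2.262/√10 = 0.715 | – | 25.9% |
| 11 | 2.228/√11 = 0.672 | −6.1% | 23.8% |
| 12 | 2.201/√12 = 0.635 | −11.2% | 22.1% |

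The average narrowing at 10% drop-out with 12 treated is 0.377 × 6.1% + 0.282 × 11.2% = 5.5%.

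**An illustration for tolerability.** Section 12.0 quotes a 17% rate of ocular burning for Restasis. If that rate applied to reservoir use (an assumption), the chance that a left-out completer had burning would be 0.377 × 0.17 + 0.282 × (1 − 0.83²) = 0.15.

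**Group mix.** I simulated 200,000 studies of 12 recruits with even accrual over 8 months, half in Group B (the documents give neither the accrual pattern nor the Group B share), 28 days to finish for Group A and 42 for Group B, and 10% drop-out. Group B made up 49.0% of the first 10 completers, against 50.0% of all completers.

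**The case against.** The rule is fixed in advance and depends on order, not results, so nobody can use it to pick favourable subjects. That stands, and no bias is alleged. If order is unrelated to outcome, the expected burning rate in the first 10 equals the rate in all completers, so the 15% figure shows what could be missed, not a distortion. The group-mix shift of one percentage point is negligible.

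The precision gain is small, the protocol calls this a small preliminary pilot, and no power target or success criterion depends on it. That also stands, and it limits the weight of the point.

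The 0.66 needs all 12 recruits to be eligible. Consent comes before the staining and OSDI checks, so some may fail. With 12 recruits and 10% drop-out, the chance of a surplus completer is 0.46 if each is eligible with probability 0.95, 0.30 at 0.90 and 0.19 at 0.85 (assumed rates). Stopping enrolment at the tenth completer would lower the 0.66 to about 0.55 under the even-accrual assumptions above, but no such stop is written. The headline probability is therefore conditional and should be read with its range.

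Adverse events are not lost. Section 13.0 requires every one to be "recorded on an Adverse Event Case Report Form regardless of whether or not they are considered to be related to the test article". The loss is in the analysed endpoints only.

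Finally, the SAP is dated 8/27/2024 and is in the past tense, so rewording 5.0 may come too late, and nothing in the documents shows that a completer was actually omitted. This shifts part of the remedy to the report. None of these objections supplies a reason for discarding complete data.

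**Conclusion.** The point holds. As written, 5.0 excludes complete data from treated, eligible subjects without giving a reason, and neither 15.0 nor the SAP covers the case. Under the plan's own 12 recruits and 10% drop-out, with all 12 eligible and treated and drop-outs independent, a surplus completer is more likely than not (0.66). Across the screen-failure and drop-out rates examined for 12 recruits, the chance runs from zero to 0.88. The cost is modest: between 0% and 11% in interval width, and up to about 4 percentage points on the zero-event bound (25.9% to 22.1%). The change is worth making because it bears on the study's main question and needs no new data. The separate exclusion of withdrawn subjects in 15.0 is not settled by this point.

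**What to change.** - In Protocol 5.0, replace the cap with a statement that 10 completers is the minimum and that all eligible subjects who complete the study are analysed. State the same analysis set in the SAP. This also removes the ambiguity over what first means.
- Report the numbers recruited, treated, completed and analysed, by Group A and Group B.
- In the report, state whether any completer was left out. If so, add an analysis of all completers, labelled as added after the fact.
- The wording above covers completers only, so it is consistent with 15.0 as it stands. If safety and tolerability are meant to cover everyone who received Restasis, 15.0 must be amended at the same time.

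The cost is one sentence in 5.0 and one in the SAP, plus one in 15.0 only if that extension is chosen. No further recruitment or visits are needed. If the analysis has already been run, it is repeated with at most about two more subjects.

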#### **6.0 Recruitment Methods**

Recruitment will begin once IRB approval has been received and will occur through BostonSight. The subject pool will consist of patients who are actively coming through the clinic. We anticipate that all our subjects will be from the current patient population at BostonSight. If a patient is interested in participating in the study, they will be directed to the principal investigator or the study coordinator who will go over the study details.

The investigator or coordinator will use the outline to determine initial eligibility. Current patients of BostonSight may also be recruited as a result of a search of the patient database and by the use of sending patient/doctor information letters and/or e-mails regarding the study.

#### **7.0 Multi-Site Research Communication – N/A**

#### **8.0 Study Timelines**

The total duration of the subjects' participation in the study will be between 4-6 weeks. It is anticipated that to enroll all study subjects, it will take approximately 8 months. The estimated date for completion of this study is 12 months after the start of recruitment.

The study will enroll 2 groups of subjects:

- Group A: Those subjects already using preservative free buffered normal saline (Purilens) at the time of enrollment to the study

- Group B: Those subjects NOT currently using preservative free buffered normal saline (Purilens) at the time of enrollment but who are willing to be switched to preservative free buffered normal saline (Purilens) as part of the study protocol

Visit 1A:

- a. Completion of informed consent
- b. Collect past medical history, past ocular history, allergies, medications as well as habitual contact lens information, including lens design, power, and diameter.
- c. Subject's evaluation of symptoms via a baseline tolerability questionnaire and baseline Ocular Surface Disease Index (OSDI)
- d. Visual acuity assessments of both eyes (logMAR)
- e. Baseline assessment of PROSE device:
  - a. Confirm acceptable fit
- f. Baseline Oculus Keratograph 5M R-Scan with lens (automatic classification of redness)
- g. Remove lens
- h. Baseline Oculus Keratograph 5M R-Scan without lens (automatic classification of redness)
- i. Baseline slit lamp examination (without lens) including:
  - a. anterior segment and ocular surface
  - b. conjunctival redness (Efron Grading Scale, Modified Efron Grading Scale)
  - c. corneal staining with sodium fluorescein (NEI Grading System)
  - d. conjunctival staining with lissamine green (NEI Grading System)
- j. Initiation of study, with either:
  - a. Group A (subjects currently using Purilens): Dispense Restasis for initiation of usage in device bowl
    - i. Instructions for use: 1 drop of RESTASIS in the lens bowl followed by filling the remainder of the lens bowl with Purilens qAM. After 6 consecutive hours of wear, remove and reapply lens with 1 drop of RESTASIS in the lens bowl followed by filling the remainder of the lens bowl with Purilens. Wear lens without removal for at least 4 more consecutive hours.
  - b. Group B (subjects NOT currently using Purilens): the subject will be provided Purilens for use over the next two weeks and return for Visit 1B
- k. Reapply lens and wait 15 minutes
  - a. Document closed vs open PROSE device system: apply lens and wait 15 minutes. Then assess whether fluorescein seeps under haptic within 5 minutes .

Visit 1B: (Group B only – 2 weeks after dispensing Purilens)

- a. Update past medical history, past ocular history, allergies, medication
- b. Subject's evaluation of symptoms via a baseline tolerability questionnaire and baseline Ocular Surface Disease Index (OSDI)
- c. Visual acuity assessments of both eyes (logMAR)
- d. Baseline Oculus Keratograph 5M R-Scan with lens (automatic classification of redness)

- e. Remove lens
- f. Baseline Oculus Keratograph 5M R-Scan without lens (automatic classification of redness)
- g. Baseline slit lamp examination (without lens) including:
  - a. anterior segment and ocular surface
  - b. conjunctival redness (Efron Grading Scale, Modified Efron Grading Scale)
  - c. corneal staining with sodium fluorescein (NEI Grading System)
  - d. conjunctival staining with lissamine green (NEI Grading System)
- h. Initiation of study for Group B:
  - a. Group B (subjects changed to Purilens at visit 1A): Dispense Restasis for initiation of usage in device bowl
    - i. Instructions for use: 1 drop of RESTASIS in the lens bowl followed by filling the remainder of the lens bowl with Purilens qAM. After 6 consecutive hours of wear, remove and reapply lens with 1 drop of RESTASIS in the lens bowl followed by filling the remainder of the lens bowl with Purilens. Wear lens without removal for at least 4 more consecutive hours.

